ending 150 days later. Participants with the discharge status of completer, non-completer with significant progress, and in-residence were coded as 1 for “retention”. Participants with the discharge status of non-completers without significant progress were coded as 0 for “non-retention”. Our examination of the survival curves revealed that group curves crossed at 50 days from the start of the intervention, which indicated the need for a piecewise model. Thus, a multivariable, 2-piece model (i.e., Piece 1 predicting outcome events during day 0 to 50 and Piece 2 predicting outcome events for days 51 to 150) was calculated. The first piece of the model coincided with the study intervention period and the second piece to the post-intervention period. Adjusted Cox proportional hazards regression (PROC PHREG), with days as the time scale, provide estimates of hazard ratios (HR) and the 95% confidence intervals (CI) for the non-retention outcome event. HR effect size estimates are categorized as small (0.77), medium (0.53), and large (0.36) (Amaro et al., 2016). We conducted logistic regression (PROC LOGISTIC) to test for group differences in satisfactory progress among the subgroup of non-completers. We used general linear mixed models (PROC MIXED) to examine differential changes in the self-reported mechanism of action variables from pre-intervention to post-intervention by group, adjusting for covariates. We used Pearson r to test for correlation between class attendance (as a dosage variable) and change in mechanisms of action measure scores. Pearson r effect sizes are small (.10), moderate (0.30), or large (0.50). All analyses were conducted in SAS version 9.4 (SAS Institute). All models used a maximum likelihood estimated approach to account for missingness.

Substance Use and Relapse

To quantify substance use at the three assessment points (baseline, postintervention, and follow-up), our trained study staff used the TLFB measure, which is a comprehensive retrospective calendar-based validated semistructured interview measure of daily substance use (29). From TLFB data, we calculated substance use from study intervention start date

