through the day of the last intervention session date (6 weeks later) and from intervention end date to 7 months later (8.5-month follow-up period in total). The interview window for postintervention assessment was 1 to 14 days after the intervention end, and for the follow-up assessment, the window was 7–9 months after the intervention end, and this variability was dependent on participant availability. This allowed for the quantification of daily substance use from study intervention start date to study end point. TLFB data allowed us to operationalize three substance use outcomes for any drug use and alcohol to intoxication as well as methamphetamine and cannabis/marijuana, including the following: time to first use, quantified as days until first any drug use or alcohol intoxication; days of use, quantified as the total number of days in which any drugs were used or alcohol intoxication occurred, and relapse status, quantified according to a) abstinent, did not use during the period after the study intervention; b) lapse, used after study intervention but did not revert to regular use on one-third or less of days after first use; and c) relapse, used substance after the study intervention and continued to use regularly on more than one-third of days from first use.

Alcohol and Drug Use Confirmation Tests

Breathalyzer (for alcohol) and urine (for drug) samples were collected at postintervention and follow-up. We calculated agreement rates for any and each drug (excluding alcohol) against TLFB self-report. Only two participants had a positive Breathalyzer result. For urinalysis, we compared TLFB drug use reports for 3 days before the urinalysis date against the urinalysis result.

Data Analysis

Our analytic sample size of 200 was powered to detect a medium-sized effect (Cox regression hazard ratio [HR] = 0.51) for days until first drug use with a two-sided $p < .05$ significance level,

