80% power, and a 35% probability of substance use in the control group. Our ITT analysis of $N = 200$ did not include the 25 women randomized to a study group who never showed up to the first class and were thus excluded from analysis based on receiving no dose of the intervention. Prediction models included clinical covariates identified a priori as having conceptual relevance for their impact on the effect of study intervention on recovery (i.e., number of mental health diagnoses coded as SUD only, one co-morbid mental health diagnosis, two or more comorbid mental health diagnoses, adult- hood trauma exposure [summed domain score from Life Stressor Checklist Revised], PTSD diagnosis via the Diagnostic and Statistical Manual of Mental Disorders [5th Edition], and PTSD symptom score [PTSD symptom Scale Self Report]). These models also adjust for an inherent study design variable (i.e., days in residential treatment before study intervention start date). Unadjusted models as effect size confirmation is located in the online supplement. We use the piecewise Cox regression PHREG procedure in SAS version 9.4 (SAS Institute) to model time periods during and after the study intervention (i.e., piece 1 predicting outcome events during the intervention period and piece 2 predicting outcome events after the intervention). Resulting HR effect sizes are interpreted as small (0.77), medium (0.53), and large (0.36) (35). Next, because of the zero-inflated distribution of days of substance use, we use negative binomial hurdle models to estimate any use (versus abstinence) and days of use among users simultaneously (36). Finally, we compute unadjusted and adjusted proportional estimates for group differences in relapse status (i.e., abstinent, lapse, relapse), and effect size is expressed as odds ratios (ORs).

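### Days of use are compared among users only, and no combined effect on days of use over all analysed women is planned

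*SAP*

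**What the plan says.** The SAP section on substance use and relapse builds three outcomes from the TLFB interview: time to first use, days of use and relapse status. The second is a raw count: "days of use, quantified as the total number of days in which any drugs were used or alcohol intoxication occurred".

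The Data Analysis section that follows gives its model in one sentence. Citing the excess of zeros, it says "we use negative binomial hurdle models to estimate any use (versus abstinence) and days of use among users simultaneously". The listed covariates are baseline clinical variables plus days in residence before the intervention began. The analysed sample is 200 women; a further 25 who were randomised but did not attend the first class are left out.

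The section names no arm comparison of mean days with abstinent women counted as zero. It also does not say how the two parts of the hurdle model are to be read together.

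**The concern.** A hurdle model gives two arm effects: one on whether a woman used at all, and one on how many days she used, given that she did. The first covers all analysed women. The second covers only women who crossed the hurdle, and crossing it happens after randomisation and is something MMWR aims to prevent. If MMWR keeps some women abstinent, the users left in that arm are no longer the counterparts of the users in the control arm. Adjusting for baseline covariates does not restore that comparability in general.

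If the women kept abstinent would otherwise have used lightly, the remaining users are on average heavier. The count-part ratio then rises although nobody used more. With no combined figure, the ratio labelled days of use is the only arm effect on days that a reader has, and it may have the wrong sign for total use.

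**Working it through.** The plan gives no power or sample-size figure for days of use, so there is no stated number to reproduce. The check asks whether the two summaries can disagree, and by how much.

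**Inputs**
- Control-group use, 35%: SAP, Data Analysis (substance use), where it supports the power statement for time to first use.
- Assumed: in the control arm, 15% of women are light users (5 days) and 20% are heavy users (60 days), together the 35%.
- Assumed: MMWR halves light use (15% to 7.5%) and leaves heavy use unchanged.
- Assumed for precision only: 100 women per arm and no variation within user type.

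**Formulas.** Users-only mean = (light share × 5 + heavy share × 60) / (light share + heavy share). All-women mean = the numerator alone.

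| | Control | MMWR | Ratio |
|---|---|---|---|
| Any use | 0.35 | 0.075 + 0.20 = 0.275 | 0.79 |
| Mean days, users only | (0.75 + 12) / 0.35 = 36.4 | (0.375 + 12) / 0.275 = 45.0 | 1.24 |
| Mean days, all women | 12.75 | 12.375 (12.38) | 0.97 |

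The all-women ratio is the product of the other two: 0.786 × 1.235 = 0.97. The reversal comes entirely from conditioning on use.

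**Precision of the users-only ratio**
- Variance among users: control (15 × 20 / 35²) × 55² = 740.8; MMWR (7.5 × 20 / 27.5²) × 55² = 600.0.
- SE of the log ratio = √[740.8 / (35 × 36.43²) + 600.0 / (27.5 × 45.0²)] = √(0.01595 + 0.01077) = 0.163.
- 95% CI = exp(0.211 ± 1.96 × 0.163), about 0.90 to 1.70.

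**Precision of the all-women ratio**
- Variance over all women: control 723.75 − 12.75² = 561.2; MMWR 721.875 − 12.375² = 568.7.
- SE of the log ratio = √[561.2 / (100 × 12.75²) + 568.7 / (100 × 12.375²)] = √(0.0345 + 0.0371) = 0.268.
- 95% CI about 0.57 to 1.64.

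**Sensitivity to the assumed mix.** Control use was held at 35%. The light/heavy pairs were 5/90, 10/60 and 20/60 days, with 30% to 70% of users light and 25% to 75% of light use prevented. The users-only ratio ran from 1.05 to 1.92 and the all-women ratio from 0.67 to 0.99. At the upper end (5/90 days, 70% light, 75% prevented) the users-only mean goes from 30.5 to 58.7.

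**Fitted model.** Zero-truncated negative binomial fits to simulated trials (100 per arm, 5/90 days, 50% or 70% of users light) gave a count-part ratio above 1 in 82% to 94% of trials when 50% to 75% of light use was prevented. With no effect (run with 50% light) the figure was 45%. Only direction is used: the quick standard errors rejected too often under no effect (9% in one direction), so the p-values are set aside.

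**The case against.** A hurdle model is a legitimate choice for counts with many zeros, and the SAP labels the count part openly as applying to users. The same model reports any use, which in the example is 35% against 27.5% in favour of MMWR. Time to first use and relapse status also cover all analysed women, so prevented use would show there too. The misreading therefore arises only when the count part is read alone. This stands, and it limits the point. But those results do not give an effect on days. Two hurdle estimates pointing in opposite directions still need a rule for combining them, and none is stated.

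The example is also chosen. Nothing in the documents suggests that MMWR would act on light users only, and the gain it hides is about 3%. This stands as well.

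A reader might go further and infer that the raw total is biased because no offset for days observed is stated, given that of the follow-up interview the SAP says "the window was 7–9 months after the intervention end, and this variability was dependent on participant availability". The documents do not support that step:
- The spread concerns interview dates. The post-intervention counting period is worded as fixed: "from intervention end date to 7 months later (8.5-month follow-up period in total" (closing bracket omitted). The later statement "This allowed for the quantification of daily substance use from study intervention start date to study end point" is loose, but it does not replace that period.
- The SAP does not say how a woman without a follow-up interview enters this model. Its only general statement, "All models used a maximum likelihood estimated approach to account for missingness", closes the retention analysis. Silence is not a decision to enter a short total as a complete one, and no follow-up rate is given.
- An offset would not cure the selection into users. It would also assume one constant rate of use across the residential and later periods. Days observed, used as a covariate in the any-use part, would itself be a post-randomisation variable.

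**Conclusion.** The point holds as a gap in reporting, of low severity. The users-only ratio is not a randomised contrast, and no combined effect on days of use is planned beside it. On the mixes tried, preventing light use alone moves the users-only ratio to between 1.05 and 1.92 while total use falls by 1% to 33%. These sizes rest on assumed user mixes and an assumed effect confined to light users; only the 35% comes from the SAP.

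It does not follow that the planned analysis would show harm, since the interval in the worked example includes 1. Nor does it follow that the hurdle model should be abandoned. The all-women ratio is no more precise (0.57 to 1.64 in the example); its merit is that it answers the question about total use without selecting on use. It still leaves out the 25 randomised women who did not attend the first class, so it is a contrast over the 200 analysed women, not over all 225.

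**What to change.** Keep the hurdle model. State that the treatment effect on days of use is the arm difference and ratio in mean days over all analysed women, with abstinent women counted as zero. To obtain it:
- For each woman, multiply the fitted probability of use by the fitted mean days given use, once under each assignment, and average over the sample.
- For the second factor use the zero-truncated mean, not the untruncated negative binomial mean parameter.
- Take the confidence interval from a bootstrap that resamples women within arm and refits both parts.

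Report the any-use effect beside it, and label the users-only ratio descriptive. Do the same for methamphetamine and cannabis if days of use are modelled for them separately. No offset and no days-observed covariate should be added on this ground.

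The cost is one post-estimation step and a sentence or two in the SAP, with no new data and no change to the model.
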